7.2.4.3 Storage of remaining biomarkers samples and additional analyses

The remaining biomarker samples (tumor, bone marrow aspirate or biopsy) may be stored for up to 15 years and further analyzed to address scientific questions related to the LEE011 and/or cancer and/or the development of biological tests. The storage of these biomarker samples for additional analyses is optional. A decision to perform such exploratory biomarker research studies would be based on outcome data from this study or from new scientific findings related to the drug class or disease, as well as reagent and assay availability.

[REDACTED]

Samples will only be stored and additional analyses will only be performed on samples from patients who agree to participate in this biomarker component by agreeing to this option in the main informed consent form.

7.2.5 Total blood volume

The total volume of blood that will be drawn from each patient in this study during the first 2 cycles (8 weeks) of treatment is shown in [Table 7-7](#).

Table 7-7 Maximum total blood volume (pediatric patients)

	Maximum Sample Volume	24 hr (Cycle 1 Day 1)		Cycle 1 (4 weeks)		Cycle 1 + 2 (8 weeks)	
		No. samples	Total volume	No. samples	Total volume	No. samples	Total volume
Hematology	1 mL	1	1 mL	4	4 mL	6	6 mL
Chemistry	1 mL	1	1 mL	4	4 mL	6	6 mL
Thyroid	1 mL	0	0 mL	0	0 mL	1	1 mL
PK	1 mL	5	5 mL	14	14 mL	16	16 mL
Total			7 mL	22 mL	22 mL	32	32 mL

For younger and/or smaller patients where collection of these samples may compromise local blood volume limits, priority for blood samples will be (1) safety, followed by (2) PK

8 Safety monitoring and reporting

8.1 Adverse events

[figure not shown]
8.1.1 Definitions and reporting

An adverse event is defined as the appearance of (or worsening of any pre-existing) undesirable sign(s), symptom(s), or medical condition(s) that occur after patient’s signed informed consent has been obtained.

Abnormal laboratory values or test results occurring after informed consent constitute adverse events only if they induce clinical signs or symptoms, are considered clinically significant, require therapy (e.g., hematologic abnormality that requires transfusion or hematological stem cell support), or require changes in study medication(s).

Except for screening failures, adverse events that begin or worsen after informed consent should be recorded in the Adverse Events CRF. Conditions that were already present at the time of informed consent should be recorded in the Relevant Medical History/Current Medical Conditions page of the patient’s CRF. Adverse event monitoring should be continued for at least 30 days following the last dose of study treatment. Adverse events (including lab abnormalities that constitute AEs) should be described using a diagnosis whenever possible, rather than individual underlying signs and symptoms. When a clear diagnosis cannot be identified, each sign or symptom should be reported as a separate Adverse Event.

Adverse events will be assessed according to the Common Terminology Criteria for Adverse Events (CTCAE) version 4.03. If CTCAE grading does not exist for an adverse event, the severity of mild, moderate, severe, and life-threatening, corresponding to grades 1 - 4, will be

used. CTCAE grade 5 (death) will not be used in this study; rather, information about deaths will be collected through the End of Treatment or Study Evaluation Forms.

The occurrence of adverse events should be sought by non-directive questioning of the patient during the screening process after signing informed consent and at each visit during the study. Adverse events also may be detected when they are volunteered by the patient during the screening process or between visits, or through physical examination, laboratory test, or other assessments. As far as possible, each adverse event should be evaluated to determine:

1. The severity grade (CTCAE grade 1-4)
2. Its duration (Start and end dates or Ongoing at End of Study).
3. Its relationship to the study treatment (Reasonable possibility that AE is related: No, Yes)
4. Action taken with respect to study or investigational treatment (none, dose adjusted, temporarily interrupted, permanently discontinued, unknown, not applicable)
5. Whether medication or therapy was given (no concomitant medication/non-drug therapy, concomitant medication/non-drug therapy)
6. Whether it is serious, where a SAE is defined as in [Section 8.2.1](#).

All adverse events should be treated appropriately. If a concomitant medication or non-drug therapy is given, this action should be recorded on the Adverse Event CRF.

Once an adverse event is detected, it should be followed until its resolution or until it is judged to be permanent, and assessment should be made at each visit (or more frequently, if necessary) of any changes in severity, the suspected relationship to the study treatment, the interventions required to treat it, and the outcome.

[figure not shown]
Progression of malignancy (including fatal outcomes), if documented by use of appropriate method (for example, as per INRC and RECIST for neuroblastoma, RANO and RECIST for primary CNS (including MRT) and RECIST criteria for all solid tumors), should not be reported as a serious adverse event.

Adverse events separate from the progression of malignancy (example, deep vein thrombosis at the time of progression or hemoptysis concurrent with finding of disease progression) will be reported as per usual guidelines used for such events with proper attribution regarding relatedness to the drug.

8.1.2 Laboratory test abnormalities

8.1.2.1 Definitions and reporting

Laboratory abnormalities that constitute an Adverse event in their own right (are considered clinically significant, induce clinical signs or symptoms, require concomitant therapy or require changes in study treatment), should be recorded on the Adverse Events CRF. Whenever possible, a diagnosis, rather than a symptom should be provided (e.g. anemia instead of low hemoglobin). Laboratory abnormalities that meet the criteria for Adverse Events should be followed until they have returned to normal or an adequate explanation of the abnormality is found. When an abnormal laboratory or test result corresponds to a sign/symptom of an already reported adverse event, it is not necessary to separately record the lab/test result as an additional event.

Laboratory abnormalities, that do not meet the definition of an adverse event, should not be reported as adverse events. A grade 3 or 4 event (severe) as per CTCAE does not automatically indicate a SAE unless it meets the definition of serious as defined below and/or as per investigator's discretion. A dose hold or medication for the lab abnormality may be required by the protocol in which case the lab abnormality would still, by definition, be an adverse event and must be reported as such.

8.2 Serious adverse events

8.2.1 Definitions

SAE is defined as one of the following:

[figure not shown]
- Is fatal or life-threatening
- Results in persistent or significant disability/incapacity
- Constitutes a congenital anomaly/birth defect
- Is medically significant, i.e., defined as an event that jeopardizes the patient or may require medical or surgical intervention to prevent one of the outcomes listed above
- Requires inpatient hospitalization or prolongation of existing hospitalization,
- Note that hospitalizations for the following reasons should not be reported as serious adverse events:
 - Routine treatment or monitoring of the studied indication, not associated with any deterioration in condition
 - Elective or pre-planned treatment for a pre-existing condition that is unrelated to the indication under study and has not worsened since signing the informed consent
 - Social reasons and respite care in the absence of any deterioration in the patient's general condition
- Note that treatment on an emergency outpatient basis that does not result in hospital admission and involves an event not fulfilling any of the definitions of a SAE given above is not a serious adverse event

8.2.2 Reporting

To ensure patient safety, every SAE, regardless of suspected causality, occurring after the patient has provided informed consent and until at least 30 days after the patient has stopped study treatment must be reported to Novartis within 24 hours of learning of its occurrence.

Any SAEs experienced after this 30 days period should only be reported to Novartis if the investigator suspects a causal relationship to the study treatment. Recurrent episodes, complications, or progression of the initial SAE must be reported as follow-up to the original episode within 24 hours of the investigator receiving the follow-up information. An SAE occurring at a different time interval or otherwise considered completely unrelated to a previously reported one should be reported separately as a new event.

Information about all SAEs is collected and recorded on the Serious Adverse Event Report Form; all applicable sections of the form must be completed in order to provide a clinically thorough report. The investigator must assess and record the relationship of each SAE to each

specific study treatment (if there is more than one study treatment), complete the SAE Report Form in English, and send the completed, signed form by fax within 24 hours to the oncology Novartis DS&E department.

The telephone and telefax number of the contact persons in the local department of DS&E, specific to the site, are listed in the investigator folder provided to each site. The original copy of the SAE Report Form and the fax confirmation sheet must be kept with the case report form (CRF) documentation at the study site.

Follow-up information is sent to the same contact(s) to whom the original SAE Report Form was sent, using a new SAE Report Form stating that this is a follow-up to the previously reported SAE and giving the date of the original report. Each re-occurrence, complication, or progression of the original event should be reported as a follow-up to that event regardless of when it occurs. The follow-up information should describe whether the event has resolved or continues, if and how it was treated, whether the blind was broken or not, and whether the patient continued or withdrew from study participation.

If the SAE is not previously documented in the Investigator's Brochure (IB) or Package Insert (new occurrence) and is thought to be related to the Novartis study treatment, an oncology Novartis DS&E department associate may urgently require further information from the investigator for Health Authority reporting. Novartis may need to issue an Investigator Notification (IN), to inform all investigators involved in any study with the same drug that this SAE has been reported. Suspected Unexpected Serious Adverse Reactions (SUSARs) will be collected and reported to the competent authorities and relevant ethics committees in accordance with Directive 2001/20/EC or as per national regulatory requirements in participating countries.

[figure not shown]
8.3 Pregnancies

To ensure patient safety, each pregnancy occurring while the patient is on study treatment must be reported to Novartis within 24 hours of learning of its occurrence. The pregnancy should be followed up to determine outcome, including spontaneous or voluntary termination, details of the birth, and the presence or absence of any birth defects, congenital abnormalities, or maternal and/or newborn complications.

Pregnancy should be recorded on a Clinical Trial Pregnancy Form and reported by the investigator to the oncology Novartis DS&E. Pregnancy follow-up should be recorded on the same form and should include an assessment of the possible relationship to the investigational treatment of any pregnancy outcome. Any SAE experienced during pregnancy must be reported on the SAE Report Form.

8.4 Warnings and precautions

No evidence available at the time of the approval of this study protocol indicated that special warnings or precautions were appropriate, other than those noted in the provided Investigator Brochure. Additional safety information collected between IB updates will be communicated in the form of Investigator Notifications. This information will be included in the patient informed consent and should be discussed with the patient during the study as needed.

9 Data collection and management

9.1 Data confidentiality

Information about study patients will be kept confidential and managed under the applicable laws and regulations. Those regulations require a signed patient authorization informing the patient of the following:

- What protected health information (PHI) will be collected from patients in this study
- Who will have access to that information and why
- Who will use or disclose that information
- The rights of a research patient to revoke their authorization for use of their PHI.

In the event that a patient revokes authorization to collect or use PHI, the investigator, by regulation, retains the ability to use all information collected prior to the revocation of patient authorization. For patients that have revoked authorization to collect or use PHI, attempts should be made to obtain permission to collect follow-up safety information (e.g. has the patient experienced any new or worsened AEs) at the end of their scheduled study period.

[figure not shown]
The data collection system for this study uses built-in security features to encrypt all data for transmission in both directions, preventing unauthorized access to confidential participant information. Access to the system will be controlled by a sequence of individually assigned user identification codes and passwords, made available only to authorized personnel who have completed prerequisite training.

9.2 Site monitoring

Before study initiation, at a site initiation visit or at an investigator's meeting, Novartis personnel (or designated CRO [Contract Research Organization]) will review the protocol and CRFs with the investigators and their staff. During the study, the field monitor will visit the site regularly to check the completeness of patient records, the accuracy of entries on the CRFs, the adherence to the protocol to Good Clinical Practice, the progress of enrollment, and to ensure that study treatment is being stored, dispensed, and accounted for according to specifications. Key study personnel must be available to assist the field monitor during these visits.

The investigator must maintain source documents for each patient in the study, consisting of case and visit notes (hospital or clinic medical records) containing demographic and medical information, laboratory data, electrocardiograms, and the results of any other tests or assessments. All information recorded on CRFs must be traceable to source documents in the patient's file. The investigator must also keep the original signed informed consent form (a signed copy is given to the patient).

The investigator must give the monitor access to all relevant source documents to confirm their consistency with the CRF entries. Novartis monitoring standards require full verification for the presence of informed consent, adherence to the inclusion/exclusion criteria and documentation of SAEs. Additional checks of the consistency of the source data with the CRFs are performed according to the study-specific monitoring plan.

9.3 Data collection

For studies using Electronic Data Capture (EDC), the designated investigator staff will enter the data required by the protocol including biomarker and PK data into the Electronic Case Report Forms (eCRF). The eCRFs have been built using fully validated secure web-enabled software that conforms to 21 CFR Part 11 requirements, Investigator site staff will not be given access to the EDC system until they have been trained. Automatic validation programs check for data discrepancies in the eCRFs and, allow modification or verification of the entered data by the investigator staff.

The Principal Investigator is responsible for assuring that the data entered into eCRF is complete, accurate, and that entry and updates are performed in a timely manner.

In addition to data entered into eCRFs, requisition forms may also need to be completed for biomarker and PK sample collection. Imaging data from the patients enrolled in the study will be collected from the Investigator sites, sent to a specialty CRO, and held centrally.

9.4 Database management and quality control

For studies using eCRFs, Novartis personnel (or designated CRO) will review the data entered by investigational staff for completeness and accuracy. Electronic data queries stating the nature of the problem and requesting clarification will be created for discrepancies and missing values and sent to the investigational site via the EDC system. Designated investigator site staff are required to respond promptly to queries and to make any necessary changes to the data.

Concomitant treatments and prior medications entered into the database will be coded using the WHO Drug Reference List, which employs the Anatomical Therapeutic Chemical classification system. Medical history/current medical conditions and adverse events will be coded using the Medical dictionary for regulatory activities (MedDRA) terminology.

Samples and/or data will be processed centrally and the results will be sent electronically to Novartis (or a designated CRO).

[figure not shown]
For EDC studies, after database lock, the investigator will receive a CD-ROM or paper copies of the patient data for archiving at the investigational site.

10 Statistical methods and data analysis

The data will be analyzed by Novartis and/or designated CRO.

It is planned that the data from participating centers in this protocol will be combined, so that an adequate number of patients will be available for analysis. The data will be summarized with respect to demographic and baseline characteristics, efficacy observations and measurements, safety observations and measurements, and all relevant PK and PD measurements using descriptive statistics (quantitative data) and contingency tables (qualitative data).

The study data will be analyzed and reported based on all patients' data of the dose escalation and expansion parts up to the time when all patients have potentially completed at least six cycles of treatment or discontinued the study. Any additional data for patients continuing to

receive study treatment past the data cutoff date for the primary CSR, as allowed by the protocol, will be reported once all patients have discontinued the study.

Unless otherwise specified, cohorts treated during the dose escalation/dose expansion with the same dose levels of LEE011 will be pooled into a single treatment group and all summaries, listings, figures and analyses will be performed by treatment group.

10.1 Analysis sets

10.1.1 Full analysis set

The FAS includes all patients who received at least one dose of LEE011. Patients will be classified according to the planned treatment. The FAS will be used for all listings of raw data. Unless otherwise specified the FAS will be the default analysis set used for all analyses.

10.1.2 Safety set

The safety set includes all patients who received at least one dose of LEE011, and have at least one valid post-baseline safety assessment. The statement that a patient had no AEs (on the AE eCRF) constitutes a valid safety assessment. Patients will be classified according to treatment received, where treatment received is defined as:

1. The treatment assigned if it was received at least once, or
2. The first treatment received in the study if the assigned treatment was never received.

10.1.3 Dose-determining analysis set

The dose-determining set consists of all patients from the safety set who either meet the following minimum exposure criterion and have scheduled safety evaluations, or experience a DLT. A patient is considered to have met the minimum exposure criterion if he received at least 16 out of the 21 planned daily doses (3 weeks on, 1 week of schedule) of LEE011 in the first 28 days of dosing.

[figure not shown]
Patients who do not experience DLT during the first cycle are considered to have sufficient safety evaluations if they have been observed for ≥ 28 days following the first dose, and are considered by both the Sponsor and Investigators to have enough safety data to conclude that a DLT did not occur.

Patients who do not meet these minimum safety evaluation requirements will be regarded as ineligible for the DDS.

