- If vomiting occurs during the course of the treatment, then no re-dosing of the patient is allowed before the next scheduled dose.
- Any doses that are missed (not taken within 6 hours of the intended time) should be skipped and should not be replaced or made up on a subsequent day.
- Patients should inform the investigational site staff of any missed or delayed doses
- Patients must avoid consumption of grapefruit products, pummelos, star-fruit, Seville oranges or products containing the juice of each during the entire study and preferably 7 days before the first dose of study medications, due to potential CYP3A4 interaction with the study medications. Orange juice is allowed.

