6.3 Dose modifications

6.3.1 Dose modification and dose delay

If a patient experiences a DLT, then treatment with LEE011 must be interrupted. For all toxicity grades, if the toxicity resolves to grade 1 or baseline within 1 week of onset, treatment may be resumed at the same or a lower dose level at the investigator's discretion and following discussion with Novartis. For toxicities that result in treatment delays of more than 7 but not more than 21 days, treatment may be resumed at a lower dose level. If a patient requires a dose interruption of > 21 days from the intended day of the next scheduled dose, then the patient must be discontinued from the study. In this event, more frequent follow up as outlined in cycle 1 to monitor this toxicity may be appropriate. Changes to the dose or schedule must be recorded on the Dosage Administration Record eCRF. All patients will be followed for AEs and for SAEs for 30 days following the last dose of LEE011.

Patients who have dose-limiting neutropenia with no other dose-limiting toxicity may receive the same dose in the next cycle with myeloid growth factor support or receive study drug at the next lower dose level. If dose-limiting neutropenia recurs after myeloid growth factor support is added, then the patient should be given the next lowest dose level for subsequent cycles and myeloid growth factor support should be administered.

Patients with extensive involvement of bone marrow who are not evaluable for hematologic toxicity but who have dose-limiting neutropenia should receive the same dose in the next cycle with myeloid growth factor support or receive study drug at the next lower dose level. Since these patients are permitted to have platelet transfusions to meet platelet criteria, no dose modifications will be made for dose-limiting thrombocytopenia.

If a patient experiences an adverse event that is considered to be related to LEE011 that requires interruption of treatment with LEE011, the following must be met in order to resume treatment with LEE011 (except for patients with bone marrow disease):

- ANC must be $\geq 1,000$ / μ l
- Platelet count must be $\geq 75,000$ / μ l
- All non-hematologic toxicities must be \leq grade 1 or returned to baseline
- Absence of any other DLTs, as described in [Table 6-2](#).

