10.4.1 Variable

The primary endpoint is the incidence of DLTs in cycle 1. Estimation of the MTD of the treatment will be based upon the estimation of the probability of DLT in Cycle 1 for patients in the DDS. This probability is estimated by the model in [Section 10.4.2](#).

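### The 16-of-21 exposure rule counts doses whatever their level, so a DLT-free child reduced early in Cycle 1 can enter the BLRM as a non-DLT at a higher dose that the child hardly took

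*Protocol*

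**What the plan says.** Four provisions of the protocol combine.

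- **Entry to the dose-determining set (10.1.3).** "The dose-determining set consists of all patients from the safety set who either meet the following minimum exposure criterion", with scheduled safety evaluations, or who have a DLT. The criterion is a count: a patient has "met the minimum exposure criterion if he received at least 16 out of the 21 planned daily doses". The text qualifies the planned doses only by the three-weeks-on, one-week-off schedule.
- **Dose label (10.1.2).** The dose-determining set is a subset of the safety set, where treatment received is defined first as "The treatment assigned if it was received at least once".
- **Reductions (6.3.1).** When a toxicity, whatever its grade, has settled inside a week, "treatment may be resumed at the same or a lower dose level at the investigator's discretion and following discussion with Novartis". Cycle 1 is not excepted.
- **Model input (10.4.1, 10.4.2).** The MTD rests on "estimation of the probability of DLT in Cycle 1 for patients in the DDS". The BLRM is fitted to the presence or absence of a DLT.

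Table 6-2 does not make a dose reduction or missed doses a DLT. Missed doses "should be skipped and should not be replaced or made up on a subsequent day" (6.1.2), so at most 21 − 16 = 5 can be lost. A DLT-free patient must also be observed for 28 days and be judged by the Sponsor and Investigators to have enough safety data to conclude that no DLT occurred. SAP 2.2 refers analysis sets to RAP Module 3 of the primary CSR, which is not among the documents supplied. SAP 5.4.1 restates the model but does not say how a patient reduced in Cycle 1 is coded.

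**The concern.** The primary endpoint is the Cycle 1 DLT rate by dose, and the escalation rule acts on the posterior probability that this rate exceeds 0.333. A child who started at one level and spent most of the cycle at the next level down says little about the higher one. Under the text as written, that child can still be recorded as a full non-DLT there. With cohorts of 3 to 6, one patient is 17% to 33% of a cohort. For DLT-free patients the error makes the assigned dose look safer than the data show, which is the unwelcome direction for overdose control.

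The case is foreseeable. Protocol 1.2.1.2 reports adult grade 3 or 4 neutropenia and/or thrombocytopenia short of the DLT criteria, increasingly frequent from 600 to 1200 mg. Table 6-1 maps dose levels 2 and 3 to adult doses of 720 and 1080 mg/d, inside that range.

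**Working it through.** **Exposure.** Inputs: 21 planned doses and the 16-dose minimum (10.1.3); levels of 280, 420 and 630 mg/m² (Table 6-1). Exposure = sum of doses taken ÷ (21 × assigned dose).

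- Implied by the count: 16/21 = 76.2%.
- Assigned 630: 4 doses at 630, 5 days held for a non-DLT toxicity, 12 doses at 420 (4 + 5 + 12 = 21 days). (4×630 + 12×420) ÷ (21×630) = 7560/13230 = 57.1%.
- One dose at 630 and 15 at 420: (630 + 6300)/13230 = 52.4%. A step from 420 to 280 gives the same ratio.

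Both patterns reach 16 doses, and both patients carry the 630 label because that dose was taken at least once.

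**Effect on overdose control.** The model is logit π(d) = log α + β log(d/580) (10.4.2). The prior is redacted, so I assumed a bivariate normal on (log α, log β) and fitted its five parameters to the 48 figures in Table 14-15 (16 scenarios, three figures each): means −1.26 and −0.94, SDs 0.95 and 1.05, correlation 0.30. The root mean square error is 1.4 percentage points. The largest miss is 4.2 points, in a scenario involving 85 mg/m² that is not used here. Two checks on P(over) at 630:

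- Scenario 4 (0/3 at 280, 0/3 at 420): fitted 10.3%, printed 10.2%.
- Scenario 14 (the same, plus 2/6 at 630): fitted about 16%, printed 16.4%.

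These rows were used in the fit, so agreement shows calibration, not independent reproduction.

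P(over) at 630, always after 0/3 at 280 and with at least the original 0/3 at 420:

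| Coding of the reduced children | Data at 420 | Data at 630 | P(over) at 630 |
|---|---|---|---|
| No DLT at 630: kept, as the text reads | 0/3 | 0/3 | about 3% |
| One excluded | 0/3 | 0/2 | about 5% |
| Two DLTs at 630: kept, as the text reads | 0/3 | 2/6 | about 16% |
| One recoded at 420 | 0/4 | 2/5 | about 19% |
| One excluded | 0/3 | 2/5 | about 21% |
| Two recoded at 420 | 0/5 | 2/4 | about 23% |
| Two excluded | 0/3 | 2/4 | about 28% |

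The limit in 10.4.2 is 25%. Only the last row passes it.

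**The case against.** The strongest reply has five parts.

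1. **The route is narrow.** At most 5 doses can be lost, so the longer-delay path in 6.3.1 (more than 7 days) normally cannot reach 16. Grade 3 or higher non-hematologic events are already DLTs apart from listed exceptions. What remains is a discretionary reduction, discussed with the Sponsor, after a short hold for a lesser toxicity. This stands: such a child can enter the model, and it does not follow that many do.
2. **Exclusion overstates the effect.** Deleting any non-DLT patient, even one fully dosed, raises P(over) by the same amount. This stands. Recoding at the dose mainly taken is the fairer measure, and it gives the smaller figures.
3. **The bias can run the other way.** The same labelling charges a DLT that follows a reduction to the higher assigned dose. This stands, and limits the downward claim to DLT-free patients.
4. **Clinical review is a safeguard.** Dose decisions use all grade 2 or higher Cycle 1 toxicity and PK (6.2.2, 6.2.2.1). The joint judgement in 10.1.3 is a further check. Neither changes the model input: the judgement asks whether a DLT occurred, and a reduced child without one would normally pass.
5. **The rule may be clear elsewhere.** Planned doses might be read as doses at the planned level, or RAP Module 3 may settle the coding. The only gloss in 10.1.3 is the schedule, and the module is not supplied, so this remains open.

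A reader might infer that the rule carried the trial past its overdose limit or made the MTD wrong. The documents support neither. They do not report any patient reduced in Cycle 1, and the one crossing requires two of four DLT-free children at one level to be reduced early and then discarded.

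**Conclusion.** The concern holds as a gap in the definition of the set that feeds the primary analysis. As written, 10.1.3 with 10.1.2 and 6.3.1 allows a DLT-free child with about 52% to 57% of planned exposure to be counted as a non-DLT at the assigned dose. For such patients the estimated overdose probability at that dose is biased down.

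In the cases worked above, one such child shifts P(over) at 630 by about 2 points when no DLT has been seen there and by 3 to 5 points at 2/6. Two recoded children bring it to about 23%, still under the limit. These figures rest on an assumed form of prior, calibrated to the protocol's own scenarios. The real bias cannot be sized because no rate of Cycle 1 reductions is given. The exposure figures are exact, but the dosing patterns behind them are constructed near the worst case. That the assigned-dose label carries from the safety set to the dose-determining set is inherited; 10.1.3 does not restate it. The gap should be closed, but it is not evidence that the dose finding failed.

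**What to change.** In 10.1.3, and in the analysis plan that applies it, state that only doses taken at the assigned level, after BSA rounding, count toward the 16. Patients with a DLT stay in the dose-determining set as now.

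Add a BLRM sensitivity run in which every patient reduced in Cycle 1, with or without a DLT, is coded at the level mainly received, or at the level in use when the DLT occurred. The run is needed because the clause alone removes DLT-free reduced patients while keeping those with DLTs, which tilts the primary estimate slightly upward.

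The cost is one clause and one extra model run. An occasional patient becomes non-evaluable, and 7.1.3.1 already provides for considering a further enrolment in that case. SAP 2.5 says that the MTD/RDE was determined before enrolment halted and that no MTD analysis is planned for the final CSR. For this trial the useful part is therefore the sensitivity run, which can still be done retrospectively, with a count of patients reduced in Cycle 1. No dosing rule changes.
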